### **10.5.3 Vital Signs**

Vital signs will be reviewed for each subject. Depending on the size and scope of changes, summaries of vital signs data over time and/or changes from baseline over time will be provided.

### **10.5.4 Electrocardiogram (ECG)**

The ECG measurements from this clinical study were performed as per standard of care for routine safety monitoring, rather than for purposes of assessment of potential QTc effect. Since these evaluations may not necessarily be performed under the rigorous conditions expected to lead to meaningful evaluation of QTc data; summaries and statistical analyses of ECG measurements are not planned, and these data would not be expected to be useful for meta-analysis with data from other trials.

### **10.5.5 Physical Measurements**

Physical examination results will be reviewed for each subject. Depending on the size and scope of change in weight and BMI, summaries may be provided.

### **10.5.6 Exposure to Investigational Product**

Descriptive statistics will be produced to describe the exposure to investigational product by dosing schedule.

A listing of the unique manufacturing lot numbers, and a listing of the subjects administered each manufacturing lot number will be provided.

### **10.5.7 Exposure to Concomitant Medication**

All medication will be coded using the WHO drug dictionary. A subject listing of all prior and concomitant medications will be presented.

## **10.6 Efficacy Analyses**

### **10.6.1 Primary Analysis**

For subjects treated at the maximum tolerated combination (combining subjects from Part 1 and Part 2), the proportion of subjects with OR (a complete or partial response to treatment) per irRECIST with corresponding 90% and 95% CI will be calculated and tabulated. For SAS code, see [Appendix A](#).

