- Group 3 will enroll up to 55 advanced NSCLC subjects with low (<50%) tumor PD-L1- expression who are naïve to anti-PD-1/PD-L1/CSF-1/CSF-1R agents. Nineteen (19) subjects will be enrolled during the first stage and treated with the AMG 820 plus pembrolizumab combination. If 3 or fewer subjects have an objective response per irRECIST then, depending on the review of all available data, further enrollment may be discontinued; otherwise, enrollment up to 55 subjects will occur.
- Group 4 will enroll up to 58 NSCLC subjects who have not responded to or have relapsed during monotherapy with anti-PD-1/PD-L1 agents and are anti-CSF-1/CSF-1R naïve. These subjects will be further distributed equally between two sub-groups (4a and 4b) depending on the PD-L1 expression in the tumor tissue: high ( $\geq 50\%$ ) and low (<50%) expression (up to 29 in each sub-group). For each sub-group, an initial set of 10 subjects will be enrolled during the first stage and treated with the AMG 820 plus pembrolizumab combination. If no subjects have an objective response per irRECIST for either subgroup then, depending on the review of all available data, further enrollment may be discontinued; otherwise, enrollment up to 58 subjects will occur.

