### 3.2 Sample Size

It is anticipated that 67 to 197 subjects will be enrolled overall in this study.

Part 1 will enroll 6 to 18 evaluable subjects. The sample size in Part 1 is based on practical consideration, and it is consistent with conventional oncology studies with the objective to evaluate the safety and tolerability of a treatment combination. With 6 subjects in a cohort, there is a 47-91% probability of observing at least one DLT if the true DLT rate is 10-33%.

Part 2 evaluation of efficacy will include at least 6 subjects from part 1 who have been treated with the recommended combination dose, and will enroll additional CRC, pancreatic cancer and NSCLC subjects up to maximum 185 subjects overall. The sample size in each group evaluated in Part 2 is chosen to test whether AMG 820 can enhance the anti-tumor activity observed historically with pembrolizumab alone and/or overcome lack of response to pembrolizumab monotherapy. For each group and sub-group enrollment may stop early due to insufficient clinical activity. The pre-planned recommendation for early termination is based on ORR (evaluated when the subjects complete at least 6 months of treatment or earlier if already reaching the recommended number of responders), nonetheless the DLRT (see Section 6.2.1.2.1) will make the decision for early termination after reviewing all available safety, efficacy, pharmacokinetic and pharmacodynamic data.

Group 1 will consist of up to 43 subjects with MMR-proficient CRC (only 18 enrolled initially in the first stage) who are naïve to anti-PD-1/PD-L1/CSF-1/CSF-1R treatment. In [Le et al, 2015](#) reported a pembrolizumab objective response rate (ORR) per RECIST1.1 and Immune-related Response Criteria (irRC) of 0% (0 of 18 patients) for MMR-proficient colorectal cancers. It is anticipated that the combination treatment of AMG 820 and pembrolizumab will have an ORR of 25% or higher in MMR-proficient CRC tumors; an ORR of 10% or less is considered to be insufficient anti-tumor activity to warrant future research. If 2 or fewer of the initial 18 subjects have an objective response then the recommendation is for enrollment to Group 1 be stopped for futility. If 8 or more of the 43 subjects have an objective response then the true ORR is determined to be >10%. This Simon Two-Stage design provides 80% power when the true ORR is 25% while maintaining a 1-sided, 5% alpha error when the true ORR is 10% or lower.

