Group 2 will consist of up to 29 subjects with advanced pancreatic cancer (only 10 enrolled initially in the first stage) who have not received prior treatment with a

PD-1/PD-L1/CSF-1/CSF-1R inhibitor. In [Brahmer et al, 2012](#) reported a pembrolizumab ORR of 0% (0 of 14 patients) for pancreatic cancer. It is anticipated that the combination treatment of AMG 820 and pembrolizumab will have an ORR of 20% or higher in pancreatic tumors; an ORR of 5% or less is considered to be insufficient anti-tumor activity to warrant future research. If none of the initial 10 subjects have an objective response then the recommendation is for enrollment to Group 2 be stopped for futility. If 4 or more of the 29 subjects have an objective response then the true ORR is determined to be >5%. This Simon Two-Stage design provides 80% power when the true ORR is 20% while maintaining a 1-sided, 5% alpha error when the true ORR is 5% or lower.

Group 3 will consist of up to 55 subjects (only 19 enrolled initially in the first stage) with NSCLC who have not received prior treatment with a PD-1/PD-L1/CSF-1/CSF-1R inhibitor, and who have tumor PD-L1 expression <50%. [Garon et al, 2015](#) reported a pembrolizumab ORR per RECIST1.1 of 13.1% (28 of 214 patients) for NSCLC patients with tumor PD-L1 expression <50%, and an ORR of 14.4% (21 of 146 patients) for those with tumor PD-L1 expression from 1% to 49%. It is anticipated that the combination treatment of AMG 820 and pembrolizumab will have an ORR of 30% or higher in low PD-L1 expressing subjects; an ORR of 15% or less is considered to be insufficient anti-tumor activity to warrant future research. If 3 or fewer of the initial 19 subjects have an objective response, then enrollment to Group 3 will be stopped for futility. If 13 or more of the 55 subjects have an objective response, then the true ORR is determined to be >15%. This Simon Two-Stage design provides 80% power when the true ORR is 30% while maintaining a 1-sided, 5% alpha error when the true ORR is 15% or lower.

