## Appendix A. Code Fragments

Provisional Code Fragments for calculating a confidence interval using the Clopper Pearson Method. The following example SAS code will be utilized for the response rate analysis providing the proportion of subjects responding to treatment with corresponding 95% confidence intervals.

```
data propci (keep = ns p low_ci upp_ci);
n=xx; * total n within the treatment group;
ns= xx; *number of responders;
p=ns/n; * response rate;
q=1-p;
lowF=FINV(0.025, 2*ns, 2*(n-ns+1)); /* use for 2-sided 95% CI */
UppF=FINV(1-0.025, 2*(ns+1), 2*(n-ns)); /* use for 2-sided 95% CI */
low_ci = 1 / (1+(n-ns+1) / (ns*lowf)); * lower CI for response rate;
upp_ci = 1 / (1+(n-ns) / ((ns+1)*uppf)); *upper CI for response rate;
if p=1 then upp_ci=1;
if p=0 then low_ci =0;
output;
end;run;
```

For 90% confidence intervals.

```
data propci (keep = ns p low_ci upp_ci);
n=xx; * total n within the treatment group;
ns= xx; *number of responders;
p=ns/n; * response rate;
q=1-p;
lowF=FINV(0.05, 2*ns, 2*(n-ns+1)); /* use for 2-sided 90% CI */
UppF=FINV(1-0.05, 2*(ns+1), 2*(n-ns)); /* use for 2-sided 90% CI */
low_ci = 1 / (1+(n-ns+1) / (ns*lowf)); * lower CI for response rate;
upp_ci = 1 / (1+(n-ns) / ((ns+1)*uppf)); *upper CI for response rate;
if p=1 then upp_ci=1;
if p=0 then low_ci =0;
output;
end;run;
```

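### The 5% alpha in SAP 3.2 holds only if the advisory stage 1 stop is followed, and the fixed-sample 90% CI in SAP 10.6.1 contains the null at the minimum success count

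*SAP*

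**What the plan says.** SAP 3.2 (like Protocol 10.2) sets the success rule for each group as a count. For Group 1: "If 8 or more of the 43 subjects have an objective response then the true ORR is determined to be >10" per cent. For Group 2: "If 4 or more of the 29 subjects have an objective response then the true ORR is determined to be >5" per cent, with the same design for 4a and 4b. For Group 3: "If 13 or more of the 55 subjects have an objective response, then the true ORR is determined to be >15" per cent. Each group's paragraph ends with an error-rate claim; for Group 1 the design has 80% power "while maintaining a 1-sided, 5% alpha error when the true ORR is 10% or lower".

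The stage 1 stop is advisory. The general paragraph of SAP 3.2 calls it a recommendation and gives the decision to the DLRT after review of all data. SAP 3.1.2 and 8.1 say the same. Group 3 is worded two ways. SAP 3.2 says that at 3 or fewer responders of 19, "then enrollment to Group 3 will be stopped for futility". SAP 3.1.2 says that if "3 or fewer subjects have an objective response per irRECIST then, depending on the review of all available data, further enrollment may be discontinued".

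The primary analysis in SAP 10.6.1 is a response proportion "per irRECIST with corresponding 90% and 95% CI will be calculated and tabulated". Appendix A gives "Provisional Code Fragments for calculating a confidence interval using the Clopper Pearson Method". The code takes only a total n and a number of responders, so neither the stage 1 size nor its boundary enters. SAP 10.6.1 does not refer back to the success counts.

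**The concern.** Two statements about the primary efficacy endpoint do not quite fit the rest of the plan.

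First, the 5% is a property of the two-stage rule with the stop in force. Part of the protection against a false positive comes from groups that stop at stage 1 and so never get the chance to reach the final count. When the stop may be overridden, 5% is no longer a ceiling, and nothing in the SAP says so.

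Second, the planned interval treats the final count as if it came from a single-stage sample. A 90% two-sided CI has 5% in each tail, the level that matches a 1-sided 5% test. At the boundary the count rule and this interval can point in opposite directions: the report would say that the true response rate is above the null, next to a 90% CI that includes the null.

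**Working it through.** **Inputs (SAP 3.2).**

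| Group | Stage 1 n1 | Stop if ≤ r1 | Total n | Success if ≥ s | Null p0 | Target p1 |
|---|---|---|---|---|---|---|
| 1 | 18 | 2 | 43 | 8 | 10% | 25% |
| 2, 4a, 4b | 10 | 0 | 29 | 4 | 5% | 20% |
| 3 | 19 | 3 | 55 | 13 | 15% | 30% |

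**Step 1: reproduce the stated figures.** With the stop followed, the probability of success at true rate p is

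T(s, r1, p) = Σ over x > r1 of b(x; n1, p) × P(X2 ≥ s − x), where X2 ~ Bin(n − n1, p).

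- Alpha, T(s, r1, p0): 0.0480, 0.0468, 0.0477.
- Power, T(s, r1, p1): 0.8003, 0.8011, 0.8006.

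The stated 5% and 80% are confirmed.

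**Step 2: stop always overridden.** Alpha becomes the single-stage tail P(X ≥ s; n, p0) = 0.0607, 0.0548, 0.0603. This is the maximum.

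**Step 3: stop sometimes overridden.** Suppose only the highest futile count (2/18, 0/10, 3/19) is ever overridden. If that always happens, alpha is T(s, r1 − 1, p0) = 0.0575, 0.0548, 0.0562. If it happens for a fraction f of those results, alpha = T(s, r1, p0) + f × [T(s, r1 − 1, p0) − T(s, r1, p0)]. Setting this to 0.05 (differences taken before rounding):

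- Group 1: f = 0.00198 / 0.00947 = 21%
- Groups 2, 4a, 4b: f = 0.00317 / 0.00792 = 40%
- Group 3: f = 0.00231 / 0.00853 = 27%

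For Groups 2, 4a and 4b, 0/10 is the only futile result, so Steps 2 and 3 coincide at f = 100%.

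**Step 4: the planned 90% CI at the minimum success count.** The Appendix A code is equivalent to: lower = Beta quantile(0.05; s, n − s + 1), upper = Beta quantile(0.95; s + 1, n − s).

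| Count | Estimate | Clopper-Pearson 90% CI | Null | 90% lower limit with one more responder |
|---|---|---|---|---|
| 8/43 | 18.6% | 9.6% to 31.1% | 10% | 11.4% |
| 4/29 | 13.8% | 4.9% to 28.8% | 5% | 7.0% |
| 13/55 | 23.6% | 14.6% to 34.9% | 15% | 16.1% |

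The null lies inside each interval, by about 0.4, 0.15 and 0.4 percentage points. The cause is the number in Step 2: the Clopper-Pearson lower limit passes p0 only when the single-stage tail falls below 0.05, and at these counts it is 0.0607, 0.0548 and 0.0603. With one more responder the null is excluded.

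**Step 5: an interval that respects the design.** Rank stage 1 stops lowest and then order by total count. The lower limit solves T(s, r1, p) = 0.05 and the upper solves 1 − T(s + 1, r1, p) = 0.05. Results at the minimum count: 10.1% to 33.3%, 5.1% to 30.8%, 15.1% to 37.6%. Each excludes the null and so agrees with the count.

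**Step 6: how often the boundary is hit.** P(exactly s, having passed stage 1) = T(s, r1, p) − T(s + 1, r1, p), before rounding.

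- At the target: 7.0%, 12.0%, 5.4%.
- At the null: 2.7%, 3.4%, 2.3%.

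**The case against.** The strongest reply is that there is no contradiction to resolve. The decision rule is a count, SAP 10.6.1 tabulates an estimate with intervals, and no passage makes the interval a test. That stands. A reader might infer that success in effect needs 9/43, 5/29 or 14/55, with power falling from 80% to 73%, 68% and 75%. That would follow only if the 90% CI were the criterion, and the documents never say it is. Nor is the planned interval invalid. Under a futility stop its lower limit errs on the cautious side: using it as the test would give alpha of 2.1%, 1.2% and 2.5%.

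On alpha, SAP 3.2 attributes the 5% to the Simon design, and its general paragraph already says that the DLRT decides. The advisory status is therefore disclosed; what is missing is the consequence. A reader might also infer that alpha will exceed 5%, or that any override of a near miss takes it there. The documents do not support either inference. They report no override, and Step 3 shows that overriding only the highest futile count must exceed about 21%, 40% or 27% of such results before 5% is passed.

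Practical reach is uncertain. The Protocol Amendment 2 rationale records the sponsor's decision to stop investigating the combination, and neither document gives enrolled numbers, so it is unknown whether any group reached its planned n. The differing Group 3 wording does not change the analysis and is editorial.

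**Conclusion.** The point holds in two limited parts, and it is minor.

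(1) The unconditional 5% in SAP 3.2 is correct only when the stage 1 stop is followed. Because the plan makes the stop advisory, the attainable maximum is 6.1% (Group 1), 5.5% (each of Groups 2, 4a and 4b) and 6.0% (Group 3), an excess of at most about 1.1 percentage points.

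(2) The only planned intervals ignore the two-stage design, so at one count per group the 90% CI contains the null that the success rule declares excluded.

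Both results assume that a group continuing to stage 2 ends at exactly its planned n; at any other n the SAP gives no critical count. The boundary probabilities also assume that the stop is followed.

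**What to change.** 1. In SAP 3.2, state that the 1-sided 5% alpha is conditional on following the stage 1 rule, and give the maximum if it is overridden: 6.1%, 5.5% and 6.0%.
2. In SAP 10.6.1, name the SAP 3.2 count as the decision rule. For groups that passed stage 1 under the rule and reached planned n, report the two-stage exact 90% CI beside Clopper-Pearson, and state the ordering used.
3. Where the rule was overridden or the final n differs from plan, report Clopper-Pearson only and state that the planned count and alpha do not apply.
4. As an editorial point, reconcile the Group 3 stage 1 wording in SAP 3.2 with SAP 3.1.2 and 8.1.

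The cost is a few sentences, one extra interval to program, and a slightly less favourable alpha statement. No data collection or design element changes.

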**Analysis will be done using local lab data ie, investigator reported.**

### **10.6.2 Secondary Analysis**

The following analyses will be done using secondary efficacy endpoint data **collected using irRECIST** for all subjects treated at the maximum tolerated combination (combining subjects from Part 1 and Part 2).

Using the Kaplan Meier estimate, the PFS at 6 and 12 months and the OS at 6 and 12 months with corresponding 90% CI will be tabulated.

Listings will be produced for all subjects indicating the OS, PFS, TTR, DOR and TTP. Kaplan Meier curves will be presented for OS, PFS, TTR, DOR and TTP with estimates for rates and 80% CI at selected weeks. TTR will also be analyzed excluding subjects that do not achieve an objective response.

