3.5 Estimated Study Duration

3.5.1 Study Duration for Subjects

The duration of screening for each subject will be approximately 28 days. The duration of treatment will vary for each subject. Subjects enrolled in Part 1 and 2 of the study can be treated for up to 24 months if treatment is tolerable and clinical benefit is observed. All subjects will complete a safety follow-up visit approximately 135 (+7) days after the last dose of study treatment. After the safety follow-up visit, depending on the duration of their treatment on the study, some subjects will enter the long-term follow-up. The goal of the long-term follow-up is to obtain disease progression and survival information for a period of 12 months after the first combination dose. The actual duration of the study for an individual subject is dependent upon the time required to assess PFS and OS at 12 months.

For subjects who continue treatment past 12 months and up to 24 months (if tolerable and clinical benefit is observed), only Visit Date, IP Administration, and AE/SAE information will be collected in EDC. Remaining follow-up to be performed per institutional standard of care.

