^j Radiographic imaging (CT or MRI) of the chest, abdomen and pelvis, and MRI of the brain if a subject has signs and symptoms suggestive of CNS metastases, are required at screening. MRI of the brain is required for all NSCLC subjects at screening. Tumor assessments must also include all other sites of disease. The screening scans must be done within 28 days prior to enrollment. During treatment, radiographic imaging (CT or MRI) of the chest, abdomen and pelvis, along with tumor assessments of all other sites of disease, (MRI of the brain if a subject has symptoms or signs suggestive of CNS metastases), will be performed independent of treatment cycle at week 10 (± 1 week), and then every 10 weeks (± 2 weeks) or more frequently if clinically indicated until confirmed PD per irRECIST or start of new anticancer treatment. Imaging should not be adjusted for cycle initiation delays and performed according to the calendar. The imaging modality selected (eg, CT or MRI) should remain constant for any individual subject. Response or progression should be confirmed by repeated radiographic imaging ≥ 4 weeks after the first indication of response or progression. Radiographic imaging is required at the safety follow-up visit if the subject ended treatment prior to confirmed PD and has not had radiographic tumor imaging performed within 6 weeks (+1 week) of the visit. The radiographic images will be submitted to a central imaging lab.

^k PK samples should be collected at the exact nominal time point as noted, where collection times are to be defined relative to the end of AMG 820 infusion. If unable to collect a PK sample at the specified nominal time point collect it as close as possible to the nominal time point and record the actual collection time. PK samples not collected at exact nominal time point will not be considered protocol deviations.

^m Safety labs should be performed and reviewed within 2 days prior to each dose.

ⁿ CEA for CRC and CA 19-9 for pancreatic cancer every 6 weeks ± 2 weeks

^o For subjects who discontinued treatment for any reason other than confirmed PD, every effort should be made to perform radiographic imaging (CT or MRI) of the chest, abdomen and pelvis, along with tumor assessments of all other sites of disease every 12 weeks until documentation of confirmed PD per irRECIST, clinical progression, start of new anticancer therapy, or up to 12 months after subject's enrollment for the study, whichever occurs first.

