7.2.4 Long-term Follow-up

After the safety follow-up visit all subjects will enter the long-term follow-up. Subjects will be contacted by clinic visit or telephone to assess survival, disease status and initiation of first subsequent anti-tumor therapy following end of AMG 820 and pembrolizumab treatment.

Contact for all subjects will be attempted every 12 weeks (\pm 28 days) following the safety follow-up visit, as applicable, until death, subject withdraws full consent, or up to 12 months after subject's enrollment for the study, whichever comes first.

For subjects who discontinued treatment for any reason other than confirmed PD, every effort should be made to perform radiographic imaging (CT or MRI) of the chest, abdomen and pelvis, along with tumor assessments of all other sites of disease every 12 weeks until documentation of confirmed PD per irRECIST, clinical progression, start of new anticancer therapy, or up to 12 months after subject's enrollment for the study, whichever occurs first.

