10.3.3 Primary Analysis

The primary analysis (primary and secondary endpoints) may be done separately for each group (eg, if the pancreatic cancer group completes target enrollment months ahead of the other cancer groups, analysis for Group 2 would be executed):

1. At 6 months: once the target enrollment is complete and each subject has been treated for at least 6 months or responded or withdrawn from the study, the analysis of the primary endpoints will occur.
2. At 12 months: once the target enrollment is complete and each subject has been treated for at least 12 months or has been followed up for PFS and OS for 12 months or withdrawn from the study, the analysis of primary and secondary endpoints (safety endpoints, ORR, PFS and OS at 6 and 12 months) will occur

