#### Investigational Product

The term 'investigational product' is used in to reference to AMG 820 in combination with pembrolizumab.

---

Last Investigational Product Dose Date

The last AMG 820 dose date for each subject is defined as the latest date AMG 820 is administered.

Objective Response as per irRECIST (irOR)

Objective response is defined as a complete response or partial response, as defined by the irRECIST. Confirmation is done by a repeat, consecutive assessment no less than 4 weeks from the date of first documented assessment.

Objective Response Rate as per irRECIST (irORR)

Immune-related ORR (irORR) is defined as the percentage of subjects with irOR.

Overall Survival Time

Overall survival time is calculated as the number of days from the first administration of AMG 820 to death or if applicable censoring [(date of death or censoring – date of first dose of AMG 820 + 1)]. Subjects who withdraw from treatment without withdrawing consent will be followed for survival status up to 12 months.

Subjects who are alive (no record of death) and are lost to follow-up will be censored at the date of last contact.

Progression-Free Survival Time per irRECIST (PFS)

Progression-free survival time is calculated as the number of days from the first administration of AMG 820 to the first assessment of disease progression as per irRECIST or death due to any cause, or if applicable date of censoring (date of progressive disease or death or censoring – first administration of AMG 820 +1).

The following censoring strategies will be used for the progression free survival analysis:

If a subject's disease has not progressed and the subject is alive, progression-free survival time will be censored at the last date they are known to be progression-free (ie, the last evaluable radiological assessment date).

If a subject has no tumor evaluation in the study, progression-free survival time will be censored at the date of the first administration of AMG 820.

Subjects who withdraw consent to participate in the study prior to disease progression will be censored at their last evaluable radiological assessment date.

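### The 12-month PFS rate is read just after the last recorded scan window, so the Kaplan-Meier estimate is distorted, in a direction that depends on an unstated rule for unconfirmed progression

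*SAP*

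**What the plan says.** - **Estimator.** SAP 10.6.2 (and Protocol 10.4.3) uses Kaplan-Meier: "the PFS at 6 and 12 months and the OS at 6 and 12 months with corresponding 90% CI will be tabulated". SAP 10.1 analyses the Part 2 groups separately.
- **Censoring.** In SAP Section 6, for a living subject without progression, "progression-free survival time will be censored at the last date they are known to be progression-free (ie, the last evaluable radiological assessment date").
- **Scan schedule.** In Table 5, footnote j of the Protocol, imaging during treatment "will be performed independent of treatment cycle at week 10 (± 1 week), and then every 10 weeks (± 2 weeks"), and it is not shifted when a cycle is delayed.
- **After month 12.** Protocol 3.5.1 says that for subjects treated past 12 months "only Visit Date, IP Administration, and AE/SAE information will be collected in EDC". For those off treatment without confirmed progression, Protocol 7.2.4 continues imaging until progression, new therapy, "or up to 12 months after subject's enrollment for the study, whichever occurs first".
- **Date of progression.** Protocol 7.4 dates it at the scan on which it is first seen. Appendix D requires a confirming scan at least 4 weeks later.
- **Timing of the analysis.** Protocol 10.3.3 runs the second analysis once "each subject has been treated for at least 12 months or has been followed up for PFS and OS for 12 months", or the subject has withdrawn.

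Neither document gives a rule for a landmark that lies beyond the last recorded scan: no nominal visit time, no grouped-time method and no minimum number at risk.

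**The concern.** An empty risk set does not by itself lower a Kaplan-Meier curve; the curve simply stays flat. The harm arises inside the week-50 window. A subject scanned clean early in the window leaves the risk set before the others have been scanned. A progression found later in the window is then divided by a smaller number at risk, although the clean subjects had passed the same visit. If the last subject scanned in the window has progressed, the curve falls to exactly 0%, however many were clean.

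PFS at 12 months is a named secondary endpoint, tabulated per group with a 90% CI. The subjects censored this way are those still on treatment without progression, who show durable benefit.

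**Working it through.** The documents state no expected 12-month PFS rate or number at risk, so there is no figure of the plan's to reproduce.

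**1. Where the last scan falls.** Table 5 puts the week-10 visit on day 64. Week 50 is 64 + 4 × 70 = day 344, with a window of days 330 to 358. Counting completed weeks instead, week 52 ends on day 364. Both readings end before day 365. Week 60 falls after it.

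**2. Who can still be at risk at day 365.** Footnote j and Protocol 7.2.3 require a scan at the safety visit, 135 (+7) days after the last dose, for subjects who stopped without confirmed progression and lack a recent scan. It falls after day 365 if the last dose was after about day 365 − 135 = 230. These subjects are the main exception.

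**3. The distortion in closed form.** Let n subjects enter the window, each with probability q of progression at that scan, on distinct dates. When k remain, the expected step is 1 − q/k, so the expected Kaplan-Meier factor is ∏(1 − q/k) for k = 1 to n, against a correct factor of 1 − q.

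| n | q | Expected factor | Correct factor | Ratio |
|---|---|---|---|---|
| 10 | 0.10 | 0.74 | 0.90 | 0.82 |
| 10 | 0.20 | 0.54 | 0.80 | 0.67 |
| 10 | 0.35 | 0.32 | 0.65 | 0.49 |

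With n = 1 the ratio is 1.00. If all scans share one date it is also 1.00, because tied events precede censoring.

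**4. Simulation of the whole rule.** Assumptions: exponential PFS; scans uniform on day 64 ± 7 and on days 134, 204, 274 and 344, each ± 14; progression dated at the scan that finds it; no deaths; no scan after month 12. The medians 3.7 and 6.3 months are the pembrolizumab NSCLC figures in Protocol 2.1.5. They give 0.5^(12/3.7) = 10.6% and 0.5^(12/6.3) = 26.7%. The 20% and 30% rates are assumptions.

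| N | True 12-month PFS | Planned estimate (mean) | Ratio | Estimate exactly 0% | Scans at nominal weeks |
|---|---|---|---|---|---|
| 55 | 10.6% | 5.6% | 0.53 | 37% of runs | 11.9% |
| 43 | 20.0% | 11.7% | 0.59 | 25% | 21.8% |
| 29 | 30.0% | 20.2% | 0.67 | 22% | 32.4% |
| 18 | 26.7% | 19.6% | 0.73 | 23% | not run |
| 10 | 10.6% | 9.1% | 0.86 | 42% (32% are true zeros) | not run |

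Nominal weeks recover true week-50 PFS (12.1%, 21.9% and 32.2% in the first three rows).

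**5. A quarter of subjects with a later scan.** The first three rows become 8.7%, 17.0% and 27.0%, or ratios 0.82, 0.85 and 0.90.

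**6. Unconfirmed progression not counted.** A progression first seen on days 330 to 358 can be confirmed no earlier than days 358 to 386, usually after month 12. If such progressions are censored, N = 55 gives 18.4% against 10.6%, a ratio of 1.74. Across the first three settings the ratio runs from about 1.3 to 1.7.

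**The case against.** The strongest reply is that the direction of the error is not fixed. SAP Section 6 counts progression as per irRECIST, and irRECIST requires confirmation. It would be inconsistent to treat scans after month 12 as lost for clean subjects while assuming that week-50 progressions are confirmed. This stands. Dating progression at first observation favours counting it, but no sentence says that an unconfirmed progression is an event.

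A reader might infer that nobody is at risk at day 365 and that the rate always falls to half to three quarters of its true value. The documents do not support that:

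- Safety-visit scans can fall after month 12, and deaths are PFS events on their own date.
- The EDC limit covers only subjects who continue treatment past 12 months, and it entered with Amendment 2. Some earlier subjects may have later scans on file; the number is not given.
- The loss is smaller in groups of 10, and the Amendment 2 rationale says the sponsor has decided to stop investigating the combination, so groups may not reach full size.
- The 20% and 30% scenarios have no source for the groups with N = 43 and N = 29. At the 2-month median PFS that Protocol 2.1.3 quotes in previously treated CRC, N = 43 gives 1.3% against 1.6%, an error of 0.3 points.

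The consequence is also limited. PFS is descriptive, stage 2 recommendations rest on ORR, and per-subject PFS listings are planned, so progression-free subjects remain visible.

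**Conclusion.** The concern holds as a defect in how 12-month PFS is estimated. The last scheduled scan before month 12 falls in a window that ends before the landmark, and the censoring rule removes most progression-free subjects inside that window.

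If progression counts when first observed, the bias is downward: about 0.5 to 0.75 of true 12-month PFS for N of about 18 to 55 at medians of 3.7 to 6.3 months, about 0.8 to 0.9 if a quarter of subjects have a later scan, and about 0.85 to 0.9 for N = 10. If week-50 progressions without a confirming scan before month 12 are not counted, the bias is upward, about 1.3 to 1.7 times.

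These sizes rest on exponential PFS and evenly spread scan dates. The mechanism needs only staggered scan dates and some progressions in the last window. The 6-month landmark is not affected in the same way, because the week-30 scan is recorded.

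**What to change.** In SAP 10.6.2, for the late PFS landmark:

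1. Place each scheduled assessment, whether progression or censoring, at its nominal week (10, 20, 30, 40, 50). Map off-schedule scans (safety visit, 12-weekly follow-up, confirmatory) by a stated window, and keep deaths at their actual date.
2. Label the result PFS at the week-50 assessment, with the number at risk.
3. State that an initial irPD at the last recorded scan is a PFS event, with a sensitivity analysis that does not count it.
4. Keep the actual-date Kaplan-Meier curve as a display.

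An interval-censored (Turnbull) estimate is a natural alternative, but only with scan dates grouped to nominal weeks first. On raw dates it has the same weakness at the end of the window. Take two subjects: one clean at day 340, the other clean at day 274 and progressed at day 350. All probability placed between days 340 and 350 gives both observations likelihood 1, so the estimate at day 365 is 0% although one of the two was clean at that visit.

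The cost is a derived visit variable, a windowing rule and a few SAP sentences, with no new data or subjects. The nominal-week rate reads slightly above true 12-month PFS: by 1.3, 1.8 and 2.4 points in the first three settings (11.9 − 10.6, 21.8 − 20.0, 32.4 − 30.0).
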